8.4. Responsibilities for Reporting Serious Adverse Events

The investigator will record all serious adverse experiences that occur during the study period in an Adverse Event log. The study period for reporting serious adverse events starts from the

time of signing consent to the final study visit. The PI will be notified of all adverse events. The Investigator will comply with regulations and RSRB policy regarding the reporting of adverse events.

9. RISK/BENEFIT ASSESSMENT

Human Subjects Involvement: This study involves human subjects; potential risks to patients, families and clinicians require careful consideration.

9.1. Risks to Human Subjects

(a) Human subject's involvement and characteristics

Study subjects are nephrologists (n=12 or more/less), CKD patients (n=60) and their caregivers (n=36 or more/less). All subjects will provide informed consent. Subjects under age 21 are excluded from the study.

(b) Potential risks

Privacy and confidentiality. There is a small potential for risk to patients and caregivers of disclosure of private material. Research staff will need to have patient and caregiver contact information including telephone number and address available for follow-up. Alternative procedures are not available.

Psychological or physical risk. There is potential risk for minor psychological discomfort among patients and caregivers while completing questionnaires or talking about symptoms of CKD, prognosis, and their other experiences during treatment for the illness. Patients and caregivers will be instructed to inform their physician as well as the research staff if they wish to refrain from discussing aspects of their illness or refuse to answer a particular question. Physical risks in this study – that is, risks associated with voluntarily responding to oral surveys and questions asked by a research assistant are low.

9.2. Adequacy of protection against risks

Privacy and confidentiality. Staff are trained regarding HIPAA and human subjects' protections regulations and procedures. Any data collected will be stripped of any identifiers; a unique ID number will be generated for each subject and all data files. The linking file containing identifiers will not be stored in the central database repository. Data will be encrypted by applying a special scrambling code that makes the data unreadable to anyone who does not have a decryption key. Authorized personnel with access to this key can unscramble it. This file will be stored on a separate server and made accessible only to database administrators with the appropriate permissions. URMIC-managed networks where data will be stored and maintained are protected by perimeter firewalls, supplemented by additional interior firewalls to protect particularly critical or vulnerable resources. During the period in which it will be necessary to keep personal identifying information for follow-up purposes, all personal electronic data will be kept in a password-protected file on a secure mainframe computer with firewall protection located behind locked doors. Paper data will be securely kept in a locked file cabinet. Subjects will be assigned identification numbers which will be used on all data; the link between name and ID number will also be kept in a separate password protected file. Participants will be advised as to the risks to confidentiality in the informed consent. No identifying information that associates names with voices will appear on transcripts of the recorded visits or on any portable electronic

equipment. All audio-recordings will be destroyed once all analyses have been completed. No identifying data will be used in any publications.

Psychological or physical risk. Staff will receive training in techniques for communicating effectively and sensitively with patients diagnosed with advanced CKD and their caregivers. Patients and caregivers will be informed that they have the right to terminate participation at any time and to refuse surveys or leave survey questions blank if they are uncomfortable for any reason. In the unlikely event of extreme psychological discomfort in a patient or caregiver, staff will be trained in procedures for ensuring necessary medical or professional intervention. The research assistants will be trained to identify and respond to emotional distress expressed during the interview. Research assistants will monitor for signs of distress (e.g., tearfulness, expression of discomfort, agitation). If a participant should become distressed, the research assistant will respond empathically and temporarily pause or stop the interview depending on the preference of the participant and the assessment of the researcher. If a participant becomes extremely distressed, the research assistant will contact [name]. If the participant is under care with a psychotherapist or psychiatrist, they will be encouraged to contact the appropriate care provider; otherwise, referrals will be provided.

9.3. Potential benefits of the proposed research to the subjects and others

Some patients benefit from knowing that their participation in studies like this can help other patients and families in the future. Adequate safeguards to minimize inherent risks are in place. We believe the potential risks to subjects are reasonable in relation to the importance of the knowledge to be gained.

9.4. Importance of the knowledge to be gained

Communication skills is a growing area of healthcare with relatively little empirical data to identify “best practices” on dialysis-related decision making. This study will help to address important gaps in the science of communication with patients with CKD.

10. CONFIDENTIALITY OF DATA AND INFORMATION STORAGE

To protect the confidentiality of participants, each participant will be de-identified and coded. These codes will not be derived from or related to the information about the individual, and cannot be translated to identify the individual. The identifying information will be kept separate from the research database. Only the PI will have the key to the codes. The codes will only be broken if there is a life-threatening result that calls for an intervention.

The research data will be stored in the locked office of the RA. Electronic version will be stored in a REDCap or a shared drive (password protected). All the files will be password protected, especially the file containing the key to the codes linking patients to their data. Paper documents will be locked in a drawer in the office of the RA. Excess copies of paper documents will be shredded. The PI and co-investigators will have access to de-identified data. Only the PI and RA will have the data with participant identifiers.

All data shared for the purpose of analysis will be de-identified and securely stored on the HIPAA-compliant UR Box.com. The storage and maintenance of data will occur within the URMCM-managed networks, which are safeguarded by perimeter firewalls. Additionally, extra interior firewalls are in place to safeguard especially critical or vulnerable resources.

11. DATA ANALYSIS AND MONITORING

11.1. Planned Statistical Analysis

This is a pilot cluster-randomized trial, where our communication outcomes (APPC scores) ³²

and shared decision-making outcomes (OPTION scores)⁴⁰ are measured at the level of the physician-patient dyad, while other outcomes (e.g., SDM questionnaire)⁴¹ are measured at the level of the patient for descriptive analyses but adjusted for the clustering effect in final analyses. All analyses will be performed using SAS (version 9.4, Cary, NC). Patient and physician characteristics will be described using proportions for categorical variables and means (\pm standard deviations) or medians (interquartile range) for continuous variables. **Quantitative analyses (Aims 1-2):** Analyses of the Feasibility and Acceptability of the Intervention Measures (**Aim 1**) will be mainly descriptive. To compare group differences for the study outcomes (**Aim 2**), we will use Wald-type tests from pre-specified mixed-effects linear regression models for continuous outcomes and generalized linear models with logit link function for binary outcomes. *Analyses will be specified to account for the nesting of patients (the units of analysis) within physicians (the units of randomization).* For all regression analyses, physician-level covariates for gender, years of experience, practice style, prior communication skills training, and the renal fellow status will be included, as well as patient-level covariates to adjust for demographic characteristics. All reported p values will be two sided, with $p < 0.05$ considered statistically significant. **Qualitative analyses (Aim 1):** Using Atlas.ti software, interviews of patients (30 minutes) and nephrologists (15 minutes) will be transcribed, de-identified, and verified for accuracy by a third party. Based on a modified phenomenological approach,¹⁵² I will work with [name], MPH (data manager), under [name] supervision, will create a coding scheme to characterize barriers, strengths, and areas of improvement for the proposed intervention and study design. Ten initial transcripts will be read and reread to reach an agreement. Disagreements will be resolved by discussion with the mentoring team. Remaining transcripts will be coded according to the coding scheme. **Handling of missing data:** The regression approach requires the "missing completely at random" (MCAR) assumption for valid inference, which may not be met for some outcomes in this study. Therefore, we will apply the response-dependent missingness—or the missing at random (MAR)—assumption when outcomes and missing data are less likely to be independent. We will examine the nature of the missing data and use the inverse probability weighting (IPW) approach, or multiple imputation, and sensitivity analyses, if necessary.

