3.2. Inclusion and Exclusion Criteria

Participant inclusion and exclusion criteria are listed in Table 4.

Table 4. Inclusion and Exclusion Criteria

	Physicians	Patients	Caregivers	Research Coordinator	Patient Coach	Physician Coach
Inclusion Criteria	
1. Member of Strong nephrology group working at Strong Memorial Hospital, Highland Hospital, FF Thompson or Rochester General Hospital
 
2. Treat patients with CKD
	
1. Age ≥ 65 years old
 
2. Presence of advanced CKD stage 4 or 5 (i.e. GFR, eGFR, or GFR by Cystatin ≤ 25 ml/min)
 
3. Patient's nephrologist is enrolled in the study and has seen that nephrologist at least once
 
4. Speaks English
 
5. Have not attended a dialysis education class or met with the dialysis education coordinator within 2 years prior to the study start date.
 
6. Have not made a dialysis decision
	
Consenting patients will be asked for permission to contact up to three caregivers, defined as a "family member, partner, friend or someone else who is involved with their health care issues, for example, someone whom they talk to about personal issues including medical decisions or who comes to doctor appointments with them. This person may also help with routine day-to-day activities, like transportation or paperwork." The term "caregiver" is used here for scientific purposes only; it is not essential that this individual self-identify as a caregiver.
 
1. Self-identified caregiver (per the definition above)
 
2. 21 years of age or older.
	
1. Assisted in the study by recruiting, consenting, and interviewing at least one subject.
	
1. Assisted in the study by completing at least one coaching session with a subject.
	
1. Assisted in the study by completing at least one coaching session with a nephrologist

Exclusion Criteria	
1. Expecting to leave in six months.
	
1. Patient has already been seen by a palliative care clinician or is enrolled in hospice
 
2. Is already on dialysis
 
3. Hospitalized at the time of recruitment
 
4. Cognitive impairment and no legally authorized representative is available
	
4. Support is offered primarily in a professional role (e.g., clergy).
 
5. Cognitive impairment
	
6. Did not recruit, consent, or interview any patients.
	
7. Did not complete any coaching sessions with patients.
	
8. Did not complete any coaching sessions with nephrologists.

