(a) value/preference clarification (b) compare options including conservative management (c) choose an option that seems to best fit with patient preferences. An effort will be made to tailor these sessions to the individual needs of a nephrologist by reviewing the identified needs and discussion with the coach. The communication coaching session will be audio-recorded, and nephrologists will receive written feedback via email following the sessions to reinforce their

learning. A manual and fidelity checklist will be developed to deliver this component of the intervention.

Patient recruitment at Strong, Highland and Rochester General Hospital will start once a nephrologist in the intervention group has completed at least two communication coaching sessions. At the end of each patient visit, nephrologists will be asked if (a) a preliminary RRT decision has been made? If not, is there a plan to discuss it in the next visit? Once a patient has made an RRT decision or has seen the nephrologist twice, either in-person or via Zoom, a final set of assessments will be completed. At the end of the study, to check for contamination, nephrologists in the intervention group will be asked if they were able to share newly learned communication skills with the nephrologists in the control group.

Upon completion of the decision-making process with the nephrologist, depending on patient's choice, patients will be given a summary of the 'next steps,' prepared in conjunction with the treating nephrologist. A copy will be given to the patient by the research coordinator in-person or via mail: (1) When does the patient need to finalize the decision (only if the decision has not been made after two visits)? (2) At what GFR level, access will be placed? (3) Symptoms suggestive of need for dialysis (4) when will dialysis need to be initiated?

Patient component (and caregivers, if available):

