Approximately, 2-4 weeks prior to the visit with a coach, patients will receive an educational booklet about renal replacement therapy options and conservative management and another booklet containing a list of most commonly asked questions. Educational booklet will also be sent in a video format. Participants in the intervention group will then meet with a coach for approximately 60-90 minutes within two weeks prior to an office visit with their nephrologist. This intervention can take place at the Strong Hospital site or an alternate location of the patient's choice. If intervention takes place at the subject's home, a room that ensures privacy and confidentiality will be requested for the process to take place. Also, if at subject's home, study activities that are being conducted will use the same methods as if on site at URM. During the first half of the coaching session, the coach will administer the value affirmation exercise, identify goals/preferences of kidney disease treatment so that they can articulate to the nephrologist and review renal replacement therapy options including conservative management with the patient. The coach will not answer any questions regarding RRT options but would rather help patients formulate questions about different RRT options including conservative management. Subsequently, the coach will give each patient (and caregiver) a list of commonly asked questions ("question prompt list" or QPL), and use brief role-plays to identify and help prepare patients to ask personally relevant questions during their upcoming nephrologist visit, so they can participate more actively and assertively in discussions with their nephrologist. If a patient has not read the education material or QPL, they will be given an opportunity to read the material or watch the video. Patient's questions along with renal and overall prognosis, using standardized tools (Schmidt RJ, Landry DL, Cohen L, et al. Derivation and validation of a prognostic model to predict mortality in patients with advanced chronic kidney disease. *Nephrology Dialysis Transplantation*. 2019;34(9):1517-1525. doi:10.1093/ndt/gfy305) (Tangri N, Stevens LA, Griffith J, et al. A predictive model for progression of chronic kidney disease to kidney failure. *JAMA - Journal of the American Medical Association*. 2011;305(15):1553-1559. doi:10.1001/jama.2011.451) will be forwarded to the nephrologist a day before the visit, either in-person or via e-mail. Patients (as well as the research coordinator) will also bring a list of their questions and visit checklist to the nephrologist. The nephrology visit will be audio recorded and the recordings will be destroyed after transcription and analyzation is complete. The coach will make a follow-up telephone call

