
(after the nephrology office visit) to address patients' concerns. Patients (and caregivers) will be eligible to attend an additional coaching session if unable to make a decision about dialysis with their nephrologist in one session. A manual and fidelity checklist will be developed to deliver this component of the intervention. Patients will be able to participate in these sessions via zoom or in-person at Strong Hospital or an alternate location chosen by the patient (ex. patient's home).

*If the research coordinator or coach will be traveling to a subject's home, in order to ensure their safety, travel to homes will only take place during daylight hours. They will also ensure that there is another team member who knows where and when they are traveling. The research coordinator or coach will also know to cut the study visit short if or when necessary and that they will have means of communication with the PI by cell phone or 911 in the case of an emergency.

In addition, no mandated reporters will be entering the subjects home at any time but if there are any problematic behaviors observed in the home, the study team member witnessing the incident will report/discuss with the PI and, if necessary, the IRB.

Control Group patients (and caregivers, if available): will meet with the dialysis educator and their nephrologist, as per the standard clinic protocol, and complete three sets of assessments. Their first set of assessments will be done at study entry, the second set will be completed within 0-3 months of seeing their nephrologist and a decision has been finalized (spanning up to two visits), and their third set will be completed at study completion which will take place within 3-6 months after their nephrology visit.

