patients, caregivers and nephrologists will be interviewed by the RA after the last meeting with the nephrologist to assess the feasibility and acceptability of the DIAL-SDM intervention. For patients in the intervention arm, the interviewer will ask open-ended questions on (1) benefits of the intervention (2) barriers to accessing DIAL-SDM (3) usefulness of the dialysis options knowledge materials (4) dialysis decision making. Interviews will be audio recorded. Similarly, patients in the control group will be asked about (1) the process of dialysis decision-making (2) experience of communicating goals and preferences with their nephrologist and if their goals were discussed during the visits with their nephrologist. Patients who decide to withdraw from the study will be interviewed when the individual confirms their withdrawal and will be asked (1) main reason for withdraw (2) suggestions for improving the study. These interviews will either take place at Strong Hospital or a location of patient's choice (ex: patient's home).

Medical Records Abstraction: We plan to record patients' labs, co-morbid conditions, advanced care planning, hospitalizations and ER visits for a total of 6 months before and 6 months after study entry on an abstraction form. This retrospective abstraction will be performed only for participants who have already enrolled and completed the study; no new patients will be recruited or consented for this purpose.

Because this is a retrospective study that involves retrospective chart review, we will also look at patient mortality, place of death, receipt of hospice services, receipt of aggressive procedures such as CPR, dialysis etc. and long-term healthcare utilization for both the control and intervention groups within 3 years of the subjects study completion date without patient consent.

Because this study involves only participants who are already enrolled and poses minimal risk, we are requesting approval to obtain HIPAA authorization verbally using a short script. This approach reduces burden for participants who have already completed study activities, while ensuring they are informed about the additional retrospective chart review.

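### The Aim 2 models pre-specify no baseline kidney-function covariate, although GFR has to be read at screening for every patient and patients are recruited after their nephrologist has been randomized

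*Combined protocol and SAP*

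**What the plan says.** Section 11.1 sets the covariates for all regression analyses. At physician level, "physician-level covariates for gender, years of experience, practice style, prior communication skills training, and the renal fellow status will be included". At patient level it continues "as well as patient-level covariates to adjust for demographic characteristics". It names no GFR, comorbidity or prognosis term, and no baseline value of the outcome.

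Elsewhere the protocol treats kidney function as central:

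- Table 4 (3.2) admits patients with "Presence of advanced CKD stage 4 or 5 (i.e. GFR, eGFR, or GFR by Cystatin ≤ 25 ml/min". It also requires that they "Have not made a dialysis decision" and excludes those already on dialysis.
- Section 4.1 has eligibility screened from the medical record, or by the site PI at Rochester General. Nephrologists are consulted on doubtful cases in order to remove patients with a favorable renal outlook, and may decline a patient who is unlikely to need dialysis.
- The next-steps summary in 5.1 includes the item "At what GFR level, access will be placed".

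On timing, 5.1 randomizes nephrologists after their own baseline data. Patient recruitment at Strong, Highland and Rochester General starts once an intervention nephrologist has completed at least two coaching sessions. At Rochester General, patients are approached only after their nephrologist has raised the study with them (4.1).

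Other severity data are planned. Table 6 collects OARS comorbidity, Karnofsky and KDQOL at study entry as potential covariates, with no arm restriction. Section 5.2 plans abstraction of labs and comorbid conditions, but "This retrospective abstraction will be performed only for participants who have already enrolled and completed the study".

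**The concern.** How close a patient is to dialysis plausibly affects whether a decision is reached, what is chosen, decisional conflict and how much prognosis is discussed. These are Aim 2 outcomes. If the arms differ in baseline kidney function, part of the arm contrast reflects that difference, and the planned models contain nothing to take it out.

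Two routes could produce a difference. One is chance, with few clusters. The other is selection: intervention nephrologists know their arm when patients are recruited, and they hold a veto that works on expected progression, which is severity itself. Randomizing nephrologists does not protect against differential recruitment after allocation.

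Aim 2 exists to produce preliminary effect sizes, and the plan intends a larger trial (2.2), so an avoidable distortion would be carried forward. For OPTION, APPC, the SDM questionnaire and the Decisional Engagement Scale, Table 6 lists no study-entry measurement, so adjustment for the outcome's own baseline is not possible there.

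**Working it through.** **Inputs from the plan.** From 3.1(a): 60 patients, about 5 per nephrologist, ICC 0.1, CV of cluster size up to 0.5, OPTION SD 11, target difference 15, alpha 0.05, stated power 80%. Number of nephrologists: 10 (Table 1), about 12 (9.1(a), and 60/5), up to 16 (3.1(a)).

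**Assumed, not in the documents.** Equal allocation and no dropout; an ICC for GFR between 0 and 0.1; a GFR-outcome correlation r of 0.3 to 0.5.

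**The plan's own figure.** The design effect is DE = 1 + ((1 + CV²)m − 1) × ICC. With m = 5, DE = 1 + (1.25 × 5 − 1) × 0.1 = 1.525. Effective n per arm = 30/1.525 = 19.7. Power for 15 points is then 99.0% (normal) or 97.0% (t, 10 df), so the stated 80% is not reproduced and is conservative. Nothing below depends on it.

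**Chance imbalance in baseline GFR.** In SD units, the SE of the arm difference is √(2 × DE/30).

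| Clusters | m | ICC of GFR | DE | SE (SD units) |
|---|---|---|---|---|
| 12 | 5 | 0 | 1 | √(2/30) = 0.258 |
| 10 | 6 | 0.1 | 1.65 | √(3.30/30) = 0.332 |
| 12 | 5 | 0.1 | 1.525 | √(3.05/30) = 0.319 |
| 16 | 3.75 | 0.1 | 1.369 | √(2.738/30) = 0.302 |

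With 12 clusters and ICC 0.1, a difference of at least 0.32 SD occurs in about 32% of trials. This only restates that 0.32 is one SE. A difference above 0.5 SD occurs in about 12% (5% if the ICC is 0).

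**Effect on an outcome.** Shift = r × imbalance, in outcome SDs; for OPTION, multiply by 11.

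- Imbalance 0.32 SD: r = 0.3 gives 0.096 SD = 1.06 points; r = 0.5 gives 0.16 SD = 1.76 points. Against 15 points, this is 7% to 12%.
- Imbalance 0.5 SD: r = 0.3 gives 1.65 points; r = 0.5 gives 2.75 points.
- If r is only 0.1, a 0.5 SD imbalance shifts OPTION by 0.55 points.

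**Precision.** A covariate with correlation r removes r² of the outcome variance: 9% at r = 0.3 and 25% at r = 0.5. The OPTION SD falls from 11 to 11√(1 − 0.09) = 10.5 or 11√(1 − 0.25) = 9.5.

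**What cannot be calculated.** The documents give nothing from which to size a systematic difference caused by the veto or by recruitment after allocation.

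**The case against.** The strongest reply is that this is a pilot whose primary aim is feasibility, acceptability and fidelity, and that the case for GFR rests on assumed correlations. Chance imbalance under randomization is already reflected in the standard error, so it is imprecision and not bias. Eligibility and the progression screen narrow the severity range. Reasons for nephrologists' refusals are recorded (4.1), so differential vetoing could be examined. Decisional conflict, prognostic discussion, goal concordance and treatment choice have entry values that could serve as adjusters.

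Most of this stands, and it limits the weight of the point. It does not remove it. The selection route is not covered by the standard error. A refusal log describes selection but does not correct an estimate. Baseline outcome values are not in 11.1 either, and do not exist for OPTION or APPC.

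Three stronger readings are tempting, and the documents do not support them:

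- *A reader might infer that the models adjust for demographics alone.* They also carry five physician-level covariates; the restriction holds at patient level only.
- *A reader might infer that severity cannot be compared between arms.* OARS, Karnofsky and KDQOL are collected at entry in both arms, and lab abstraction has no arm restriction. The limit to completers applies to both arms. It matters because section 7 allows withdrawal when acute worsening requires hemodialysis, so some of the sickest patients could lack abstracted labs.
- *A reader might infer that prognostic scores produced for one arm prevent adjustment.* In 5.1, "Patient's questions along with renal and overall prognosis, using standardized tools" describes information sent to the nephrologist as part of the intervention. Control patients "will meet with the dialysis educator and their nephrologist, as per the standard clinic protocol, and complete three sets of assessments", with no score mentioned. That is part of the treatment contrast and leaves adjustment for GFR open.

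**Conclusion.** The point holds as a gap in model specification. Section 11.1 names no baseline kidney-function covariate, although the value has to be looked up for every patient and the design allows recruitment to differ by arm on expected progression. Any severity difference would be left unadjusted in the Aim 2 effect sizes.

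The documents do not show that such a difference will arise, so it would be wrong to call the estimates confounded. The illustrative shift of 0.10 to 0.16 SD rests on an assumed GFR ICC of 0.1, an imbalance of one SE and correlations of 0.3 to 0.5, and describes chance imbalance only. The likely gain is modest. The change is worth making because it costs almost nothing and has to be pre-specified to be credible.

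**What to change.** 1. Keep the qualifying GFR value, its method and its date as a study-entry variable for all enrolled patients in both arms, not only completers.
2. Report it by arm with the other baseline characteristics.
3. In 11.1, add baseline GFR as one pre-specified continuous patient-level covariate in the Aim 2 models. Because Table 4 accepts three measures, use one common measure, such as eGFR, wherever it is available, and state what is used otherwise.

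The cost is one case-report entry and one sentence in 11.1. Statistically it takes one patient-level degree of freedom out of roughly 60 − 12 = 48, before the demographic covariates are counted, and mixed GFR methods add some noise. A value held for everyone enrolled could also inform the weighting or imputation models that 11.1 proposes for missing outcomes.

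Adjustment removes only the linear part of a difference in measured GFR. It does not correct selection on other aspects of expected progression, so the refusal reasons should still be tabulated by arm. Prognostic scores need not be computed in the control arm.
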